 - e. Hypertension with systolic >165 mm Hg
5. Willingness and able to remain on anti-coagulation therapy for a minimum of 3 months post procedure for all subjects and at least 12 months post procedure if the patient is on anti-coagulation pre-procedure or has CHADS₂ score ≥ 2 .
6. Left atrial diameter < 6.0 cm via transthoracic echo; or <6.5 cm via CT or MRI up to 3 months pre-procedure with documented image of largest dimension, or intra-procedural ICE or atrial angiogram if CT/MRI not available.
7. Sustained AF (>5 min uninterrupted) during the electrophysiology procedure. If the subject is not experiencing spontaneous, sustained AF, it may be induced by burst pacing (typically, from the coronary sinus) with or without isoproterenol infusion in conventional clinical fashion.
8. Women without childbearing potential, (surgically sterile or have been without a period for 12 months), or women of childbearing potential who are not pregnant per a serum HCG laboratory test.
9. Willingness, ability and commitment to participate in baseline and follow-up evaluations without participation in another clinical trial which may confound the results of this study, unless approved by the Sponsor.
10. Informed consent in writing from patient.

Exclusion Criteria:

Subjects must NOT meet any of the following exclusion criteria:

1. Presence of structural heart disease of clinical significance including:
 - a. Coronary artery disease with either:
 - o Coronary artery bypass surgery (CABG) within the last six months, or
 - o Stable/unstable angina or ongoing myocardial ischemia
 - b. Congenital heart disease where either the underlying abnormality or its correction prohibits or increases the risk of ablation.
2. NYHA Class IV.
3. Ejection fraction < 35% (within previous 3 months).
4. Previous AF ablation.
5. History of myocardial infarction (MI) within the past three months.
6. Any concomitant arrhythmia or therapy that could interfere with the interpretation of the results from this study.
7. ASD closure device, LAA closure device, prosthetic mitral or tricuspid valve, and permanent pacemakers or defibrillator leads.
8. Untreatable allergy to contrast media.
9. Severe electrolyte abnormalities at time of the ablation procedure or atrial fibrillation secondary to electrolyte imbalance, thyroid disease, or reversible non-cardiac cause.
10. Atrial fibrillation from a reversible cause (e.g., surgery, hyperthyroidism, pericarditis).

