7 ENDPOINTS

7.1 PRIMARY SAFETY ENDPOINTS

Safety shall be evaluated both acute (in hospital) and long term.

Table 1 – Primary Safety Endpoints

Endpoint	Description
Acute success	Freedom from serious adverse events related to the procedure within 7-10 days of the procedure.
Long-term success	Freedom from procedure-related serious adverse events (including those related to repeat procedures) within one year of the initial procedure.

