8 SELECTION, DISCONTINUATION, AND WITHDRAWAL OF SUBJECTS

8.1 SELECTION CRITERIA

The criteria listed below shall be used to determine if a participant is eligible for entry into the study. A subject must meet ALL of the study inclusion criteria and NONE of the study exclusion criteria in order to be considered eligible for participation.

A. *Inclusion Criteria*

Subjects are required to meet the following inclusion criteria:

1. Male or female 18 – 80 years of age.
2. Experiencing at least two (2) documented episodes of persistent atrial fibrillation (including long standing persistent) during the 3 months preceding study entry with clinical indication for AF ablation per guidelines. At least one episode should be documented by rhythm strip or ECG. Persistent AF is defined as continuous AF that is sustained beyond seven days (long standing persistent is >12 months). Episodes of AF in which a decision is made to electrically or pharmacologically cardiovert the patient after ≥48 hours of AF, but prior to 7 days, should also be classified as persistent AF episodes.
3. Refractory, contraindicated, or intolerant to Class I or III anti-arrhythmic medications. Drug doses must be therapeutic and stable.
4. Novel Oral Anticoagulant (e.g. dabigatran, rivaroxaban, apixaban), Warfarin (therapeutic INR ≥ 2.0 for at least three weeks prior to randomization), or other similar standard-of-care oral anticoagulant therapy is required (aspirin is not considered similar) for those subjects who meet two or more of the following criteria:
 - a. Age 65 years or older
 - b. Diabetes
 - c. Coronary artery disease (CAD)
 - d. Congestive heart failure
 - e. Hypertension with systolic >165 mm Hg
5. Willingness and able to remain on anti-coagulation therapy for a minimum of 3 months post procedure for all subjects and at least 12 months post procedure if the patient is on anti-coagulation pre-procedure or has CHADS2 score ≥ 2.
6. Left atrial diameter < 6.0 cm via transthoracic echo; or <6.5 cm via CT or MRI up to 3 months pre-procedure with documented image of largest dimension, or intraprocedural ICE or atrial angiogram if CT/MRI not available.
7. Sustained AF (>5 min uninterrupted) during the electrophysiology procedure. If the subject is not experiencing spontaneous, sustained AF, it may be induced by burst pacing (typically from the coronary sinus) with or without isoproterenol infusion in conventional clinical fashion.

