Total RF ablation time	
Total RF ablation time as measured by total time of ablation lesion applications, from first ablation lesion to end of last lesion, will be documented. These values will be noted in both the FIRM-guided and conventional ablation groups. If ablation for AT/atrial flutter is pursued, this ablation time will be documented separately

Total procedure time	
Total procedure time defined as: time from insertion of first sheaths for vascular access to removal of sheaths.

Medication administration	
Cardiac medications administered during the procedure including drug name, dosage, and indication and will be recorded.

Devices and equipment	
Devices and equipment used during the procedure including access devices, diagnostic and ablation catheters, and mapping equipment type will be recorded.

D. Post-procedure & Discharge Requirements

The measurements and evaluations that will occur at post-procedure are provided below.

- Post-ablation and following recovery from anesthesia, subjects will be monitored until stable.
- Once the sheaths have been removed and hemostasis has been achieved, heparin or LMWH will be restarted along with oral anticoagulation (warfarin or novel oral anticoagulants (e.g. dabigatran, rivaroxaban, apixaban)).

The platelet inhibitor (if administered during the procedure) and heparin or LMWH will be continued until the INR exceeds 2.0 (in the case of warfarin use for longer term oral anticoagulation).

Oral anti-coagulation will continue for at least three months after the procedure. Subjects who were on oral anticoagulation pre-procedure will be maintained on anticoagulation for the duration of the study.

Note: Oral Glycoprotein IIb/IIIa Inhibitors use is discouraged during the follow-up period.

- Post-procedure drug therapy will include re-initiation and/or continuation of any pre-procedure cardiac medications including all anti-arrhythmic drugs used for the treatment of atrial flutter or other arrhythmias/cardiac diseases. Supplemental anti-arrhythmic medications will be administered under the direction of the investigator and documented in the appropriate section(s) of the case report forms.

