13.4 PROTOCOL DEVIATIONS

A protocol deviation is defined as any event where the clinical investigator or site personnel did not conduct the study according to the protocol.

Investigators can only initiate deviations from the protocol where necessary to protect the life or physical wellbeing of a subject, i.e., in an emergency. Protocol deviations shall be reported to the Sponsor regardless of whether medically justifiable, pre-approved by the Sponsor, or taken to protect the subject in an emergency. Subject-specific deviations will be reported on the eCRF. Non-subject specific deviations, (e.g., unauthorized use of a study device by a physician who has not signed an investigator agreement, etc.), will also need to be reported to the Sponsor. All deviations, regardless of major / minor or pre-approved, will be reported on the eCRF. Investigators will also adhere to procedures for reporting study deviations to their IRB/EC in accordance with their specific IRB/EC reporting policies and procedures.

Regulations require that investigators maintain accurate, complete and current records, including documents showing the dates of and reasons for each deviation from the protocol.

- **Definitions**

For reporting purposes, the Sponsor classifies study deviations as major or minor:

- Major deviation: Any deviation from subject inclusion and exclusion criteria; subject informed consent procedures (e.g., failure to obtain informed consent or failure to obtain informed consent prior to study entry); randomization errors; failure to report SAE's, unanticipated adverse device effects, and deaths within applicable regulatory timeframes; device accountability issues (e.g., missing or lost investigational product); or device misuse / unauthorized device use.
- Minor deviation: Deviation from a protocol requirement such as incomplete/ inadequate subject testing procedures, non-compliance with medication regimens, follow-ups performed outside specified time windows, etc.

The Sponsor will continuously monitor site compliance. The site will receive a list of site-specific study deviations on an annual basis as part of the Annual Progress Report and as part of the Final Report upon completion of the study.

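### Section 10.2 D drops the CHADS2 ≥ 2 trigger of inclusion criterion 5, so it permits stopping anticoagulation at 3 months where the entry rule foresees at least 12

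*Protocol*

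**What the plan says.** Inclusion criterion 5 appears in the Protocol Synopsis (section 3) and in section 8.1. Its first part applies to everyone: "Willingness and able to remain on anti-coagulation therapy for a minimum of 3 months post procedure for all subjects". Its second part lengthens the period to "at least 12 months post procedure if the patient is on anti-coagulation pre-procedure or has CHADS2 score ≥ 2". The two conditions are joined by *or*, so either is enough.

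Section 10.2 D (Post-procedure & Discharge Requirements) turns this into a treatment instruction. It sets the general minimum, "Oral anti-coagulation will continue for at least three months after the procedure", and then one rule for longer treatment: "Subjects who were on oral anticoagulation pre-procedure will be maintained on anticoagulation for the duration of the study". CHADS2 is not mentioned there. It appears nowhere in the protocol outside criterion 5, and the follow-up requirements in section 10.3 give no anticoagulation duration.

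Criterion 4 in section 8.1 decides who must already be anticoagulated at entry: "oral anticoagulant therapy is required (aspirin is not considered similar) for those subjects who meet two or more of the following criteria". The five listed items are age 65 or older, diabetes, coronary artery disease, congestive heart failure, and "Hypertension with systolic >165 mm Hg".

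**The concern.** Criterion 5 tests willingness at entry. The section that should act on that willingness covers only one of the two groups from whom the longer commitment was sought. The CHADS2 trigger adds something only for subjects who were not anticoagulated beforehand, and that is exactly the group 10.2 D leaves out.

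What is at stake is subject protection and consistent conduct at up to 25 sites. One site may stop at month 3 in line with 10.2 D while another, reading criterion 5 as a treatment rule, continues to month 12. Section 11.3 lists thromboembolism and stroke/TIA among the anticipated events.

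Section 13.4 counts "non-compliance with medication regimens, follow-ups performed outside specified time windows" among minor deviations, but a stop at month 3 in such a subject complies with 10.2 D and need not be reported as one.

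The statistical reach is narrow. The effectiveness endpoints and the 10-day safety endpoint are not affected. The long-term safety endpoint is "Freedom from procedure-related serious adverse events (including those related to repeat procedures) within one year of the initial procedure", so a late event counts only if it is serious and judged procedure-related.

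**Working it through.** The protocol gives no figure to reproduce. The check compares the texts and then asks whether the gap can contain anyone.

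**Step 1. Minimum duration by subject type**

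| Subject | Criterion 5 | Section 10.2 D |
|---|---|---|
| On oral anticoagulant before, any CHADS2 | at least 12 months | duration of the study |
| Not anticoagulated before, CHADS2 < 2 | at least 3 months | at least 3 months |
| Not anticoagulated before, CHADS2 ≥ 2 | at least 12 months | at least 3 months |

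Only the last row differs in substance. The difference is 12 − 3 = 9 months, and 9 / 12 = 75% of the 12-month follow-up stated in section 6.3.

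**Step 2. Does criterion 4 already put everyone in the last row on an oral anticoagulant?**

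The protocol does not define CHADS2. I assume the usual scoring: one point each for heart failure, hypertension, age 75 or older, and diabetes, and two points for stroke or TIA. Exclusion criterion 15 removes prior stroke or TIA, so a score of 2 needs two of the other four items. That gives six pairs:

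- Heart failure + age, heart failure + diabetes, age + diabetes: each meets two criterion 4 items, so an oral anticoagulant is already required.
- Hypertension + heart failure, hypertension + age, hypertension + diabetes: if systolic pressure is 165 mm Hg or below, hypertension does not count under criterion 4. Only one item is then met, unless the subject has another, such as coronary artery disease or age 65 or older.

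For example, a 76-year-old with hypertension and a systolic pressure of 150 mm Hg scores 2 but meets one criterion 4 item (age). Criterion 4 does not require an oral anticoagulant. So three of the six pairs can leave a subject uncovered.

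**Step 3. Does any other text close the gap?**

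Section 10.1 B leaves anticoagulation before the procedure to the investigator's own standard criteria and does not tie it to CHADS2. It will put many higher-risk subjects on an oral anticoagulant, and 10.2 D then keeps them on it, but it does not guarantee this for all.

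**Step 4. A second, smaller mismatch**

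Criterion 5 refers to anticoagulation of any kind before the procedure, whereas 10.2 D refers to oral anticoagulation. Section 10.1 B allows subcutaneous low-molecular-weight heparin as an alternative. A subject on heparin alone meets the first trigger of criterion 5 but not that of 10.2 D.

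**The case against.** The strongest reply is that the texts do not contradict each other. Both set minimums, 12 months of therapy satisfies both, and nothing in 10.2 D tells anyone to stop at month 3. Criterion 5 concerns willingness and ability and is not a treatment order. Section 12.1 binds investigators to the whole protocol, and they apply criterion 5 to every subject. All of this is correct. It limits the point to what 10.2 D permits. It does not supply the missing instruction.

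Second, the affected group is narrow. Prior stroke or TIA is excluded, half of the CHADS2 pairs are caught by criterion 4, and the rest must also have fallen outside the investigator's own criteria. This stands, and it keeps the weight low. The group is nevertheless not empty under the assumed scoring.

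Third, the 9 months is a difference between stated minimums and does not measure therapy actually lost. This also stands. The protocol offers no basis for estimating how many subjects would stop early or how many events would follow.

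Fourth, a deviation under section 13.4 is judged against the whole protocol, and the Schedule of Assessments lists concomitant cardiac medications at each follow-up visit, so a stop could be noticed. That is possible. Whether it counts as a deviation would still depend on reading an entry criterion as a treatment rule, which is the ambiguity at issue.

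**Conclusion.** The point holds as a low-weight matter of patient safety and consistency that should be corrected. Section 10.2 D is the only operative instruction on the duration of anticoagulation, and it leaves out one of the two triggers in the protocol's own entry rule. For an affected subject the stated minimum is 3 months instead of 12. The number of affected subjects is unknown and probably small.

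The text comparison needs no assumption. The showing that the group is not empty rests on the usual CHADS2 scoring. No effect on sample size, power, the effectiveness analysis or the comparison between arms is claimed.

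**What to change.** Reword the 10.2 D sentence on longer treatment to carry both triggers, for example: *Any subject anticoagulated before the procedure, and any subject with a CHADS2 score of 2 or more, continues anticoagulation until study exit and for no less than 12 months after the procedure.* Leave the three-month minimum for all subjects and criterion 5 as they are.

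Two details are deliberate. Omitting *oral* from the description of earlier treatment matches criterion 5 and covers subjects on heparin alone. Stating 12 months matters because the 12-month visit may fall up to 4 weeks early (section 10.3, Table 8), so study exit alone could come before 12 months. For such a subject the duty would run up to 4 weeks past the last visit, as criterion 5 already implies.

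The cost is one sentence. CHADS2 must already be known to apply criterion 5, so no new visits, data or analyses are needed.

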10.3 FOLLOW-UP REQUIREMENTS

- ***Follow-Up Visit Schedule***

Each enrolled subject will return for visits with the electrophysiologist in accordance with Table 8 below. The day of the study procedure represents Day 0. Study visits that do not occur within the below time windows will be considered protocol deviations.

Table 8 Follow-up (FU) Visit Windows

Visit	Allowed Visit Date Range
Day 7 to 10 days (Phone or visit)	N/A
1 month (30 days)	± 1 week
3 months	± 2 weeks
6 months	± 2 weeks
12 months	± 4 weeks

- ***Resolution Period***

Following ablation treatment, subjects will undergo a 90-day "resolution" period (aka "blanking period") where medical therapy may be optimized and where any of the procedurally-derived arrhythmias that commonly follow ablation procedures may resolve.

Note: During the 90-day resolution period, medications may be adjusted as medically indicated, and as indicated in above section. Any clinically indicated changes must be documented along with the reason for change.

- ***Anti-arrhythmic Medications***

Anti-arrhythmic medications can be discontinued anytime from Day 91 to Day 180 post-procedure. The date of discontinuation will be determined by each investigator on a patient-by-patient basis, but must occur sometime from Day 91 to Day 180 post-procedure.

- ***Recurrence of AF***

If re-ablation for AF is necessary after documentation of the recurrent arrhythmia has occurred, the patient will be considered a primary efficacy study failure but still followed up for AF burden.

A. Day 7-10 Days Follow-up

(Phone Call or visit at investigator's discretion)

- Subjects will be asked if they have experienced any untoward medical occurrences since the study procedure. If so, these events will be recorded on the Adverse Event form.
- Symptom and rhythm assessment.

B. One-Month Follow-up (± 1 week)

The following assessments/procedures will be performed:

- Diagnostic 12-lead ECG
- At least 24-hr ambulatory continuous ECG monitor (Holter) or CIED interrogation, if applicable
- EQ-5D and AFEQT Quality of Life surveys
- Symptom and rhythm assessment
- Concomitant anti-arrhythmic medications
- Adverse event documentation

C. Three-Month Follow-up (+ 2 weeks)

The following assessments/procedures will be performed:

- Diagnostic 12-lead ECG

- At least 24-hr ambulatory continuous ECG monitor (Holter) or CIED interrogation, if applicable
- EQ-5D and AFEQT Quality of Life surveys
- Symptom and rhythm assessment
- Concomitant anti-arrhythmic medications
- Adverse event documentation

D. Six-Month Follow-up (± 2 weeks)

The following assessments/procedures will be performed:

- Diagnostic 12-lead ECG
- At least 24-hr ambulatory continuous ECG monitor (Holter) or CIED interrogation, if applicable
- EQ-5D and AFEQT Quality of Life surveys
- Symptom and rhythm assessment
- Concomitant anti-arrhythmic medications
- Adverse event documentation

E. Twelve-Month Follow-up (± 4 weeks)

The following assessments/procedures will be performed:

- Diagnostic 12-lead ECG
- At least 24-hr ambulatory continuous ECG monitor (Holter) or CIED interrogation, if applicable
- EQ-5D and AFEQT Quality of Life surveys
- Symptom and rhythm assessment
- Concomitant anti-arrhythmic medications
- Adverse event documentation

F. Unscheduled Follow-up Visit

The following assessments/procedures will be performed, if possible:

- Diagnostic 12-lead ECG
- At least 24-hr ambulatory continuous ECG monitor (Holter) or CIED interrogation, if applicable
- EQ-5D and AFEQT Quality of Life surveys
- Symptom and rhythm assessment
- Concomitant anti-arrhythmic medications
- Adverse Event documentation

11 ADVERSE EVENTS

At enrollment, time of procedure, and at each post-procedure visit the subject will be evaluated for any complications or adverse event. The Investigator will be required to provide the Sponsor with any information concerning any

findings that suggest any adverse events/complications pertinent to the investigation. All AEs occurring during the study will be recorded on the appropriate e-CRFs.

Subjects will be carefully monitored during the study for possible AEs. Any AE observed will be fully investigated by the Investigator and classified in line with the definitions below. All adverse events will be followed until resolution or until the Investigator judges the outcome to be chronic or stable.

11.1 DEFINITIONS

Adverse events will be reported and classified by the Investigator using the specific signs, symptoms or abnormal laboratory values, or medical diagnosis if no signs, symptoms or abnormal laboratory values can be identified. The Investigator will classify the adverse events based on the definitions as follows (EN ISO/FDIS 14155:2010):

- **Adverse Event (AE)** - Any untoward medical occurrence, unintended disease or injury or any untoward clinical signs (including an abnormal laboratory finding) in subjects, users or other persons whether or not related to the investigational medical device.
- NOTE 1: This includes events related to the procedures involved.
NOTE 2: For users or other persons this is restricted to events related to the investigational medical device.
- **Adverse Device Effect (ADE)** - Adverse Event related to the use of a medical device. This includes:
 - Any adverse event resulting from insufficiencies or inadequacies in the instructions for use, the deployment, the implantation, the installation, the operation, or any malfunction of the medical device.
 - Any event that is a result of a use error or intentional misuse.
- **Serious Adverse Event (SAE)** - Adverse Event that
 - Led to death
 - Led to a serious deterioration in the health of the subject that either:
 - resulted in a life-threatening illness or injury*, or
 - resulted in a permanent impairment of a body structure or a body function, or
 - required in-patient hospitalization or prolongation of existing hospitalization, or
 - resulted in medical or surgical intervention to prevent life threatening illness or injury or permanent impairment to a body structure or a body function**.

- Led to fetal distress, fetal death or congenital abnormality or birth defect

NOTE 1:

* In this context, the term refers to an event in which the subject was at immediate risk of death at the time of the event; it does NOT refer to an event that might have caused death if it were more severe.

** For example, if the occurrence of a “catheter insertion site hematoma” or an “AV fistula” requires a blood transfusion and/or surgical repair, it should be considered a serious adverse event.

NOTE 2:

- Preplanned hospitalizations for pre-existing condition, or a procedure required by the protocol, without a serious deterioration in health, is not considered to be a serious adverse event. For example, repeat ablation for recurrence of AF would not be considered an SAE.
- Emergency room visits that do not result in hospitalization (i.e., an overnight stay) should be evaluated for one of the other serious outcomes to determine if they qualify as SAEs.
- **Serious Adverse Device Effect (SADE)** – Adverse device effect that has resulted in any of the consequences characteristic of a serious adverse event.
- **Unanticipated Adverse Device Effect (UADE)** - Serious adverse device effect which by its nature, incidence, severity or outcome has not been identified in the current version of the risk analysis report.

